	In addition to the two study visits, the study nurse coordinator is in weekly contact with study participants and all adverse events are recorded on case report forms. The safety data including all adverse events are reviewed monthly by the investigators. The only significant potential risk directly associated with this study is that of severe hypoglycemia, if the insulin dose is too high for the subjects. In fact, we have now studied 24 subjects and have not had one single episode of severe hypoglycemia, so the risk is low. The only adverse events that have occurred are respiratory infections as is expected in cystic fibrosis. The investigators are all pediatric endocrinologists, well experienced with insulin administration and management of hypoglycemia. Efficacy data will not be reviewed until study end. No conditions have been identified that would trigger an immediate suspension of the research.....	18
17.	Provisions to Protect the Privacy Interests of Participants	18
18.	Compensation for Research-Related Injury	19
19.	Consent Process	19
20.	Setting.....	21
21.	Multi-Site Research	21
22.	Resources Available.....	21
23.	References	22

PROTOCOL TITLE: The Impact of Insulin Therapy on Protein Turnover in Pre-Diabetic Cystic Fibrosis Patients

VERSION DATE: 28 June 2021

ABBREVIATIONS/DEFINITIONS

- CF – Cystic Fibrosis
- CFRD – Cystic Fibrosis Related Diabetes
- CGM – Continuous Glucose Monitor
- BMI – Body Mass Index

PROTOCOL TITLE: The Impact of Insulin Therapy on Protein Turnover in Pre-Diabetic Cystic Fibrosis Patients

VERSION DATE: 28 June 2021

1. Objectives

1.1 Purpose: The current protocol describes a double-blind, placebo-controlled trial to determine whether insulin therapy improves protein catabolism in youth with CF and abnormal glucose tolerance, and to explore differences in efficacy between multiple daily pre-meal insulin dosing (as is currently standard for early CFRD) versus a more convenient once daily basal insulin dose (as has been used in small uncontrolled pilot studies). The findings of this study will provide a mechanistic rationale for instituting insulin in youth with CF and pre-diabetes, and will inform both research studies and clinical practice as to the best regimen for insulin delivery in this population.

Specific Aim 1

To conduct a double-blind, placebo-controlled study of the impact of daily insulin therapy on meal stimulated protein turnover in 60 youth age 10-25 years with CF and abnormal glucose tolerance. Assessment will occur before and after 1 month of insulin therapy.

Hypothesis 1: In this insulin insufficient CF population, daily insulin replacement therapy will reduce meal stimulated protein catabolism from pre-insulin baseline, and will produce greater reductions from baseline than in placebo-treated patients.

Specific Aim 2

To ascertain differences in the impact of 1X daily basal insulin versus 3X daily rapid-acting insulin on meal stimulated protein turnover in 60 youth age 10-25 years with CF and abnormal glucose tolerance.

Hypothesis 2: A single daily dose of basal insulin will safely provide the same therapeutic benefit as the current standard method of insulin delivery of pre-meal 3x daily rapid acting insulin.

Specific Aim 3

In a novel exploratory aim, we will assess the turnover of 3 individual proteins previously implicated in CF pathophysiology--- albumin, transferrin, and clusterin--- to determine the extent to which their synthesis and accumulation differs at baseline from normal controls and is subsequently affected by insulin therapy. Twenty matched healthy controls will be assessed at baseline only (no insulin therapy).

2. Background

2.1. Significance of Research Question/Purpose: Given the universal prevalence of insulin insufficiency in CF, the high lifetime risk of developing diabetes, the clinical impact of insulin insufficiency on protein catabolism and survival in CF, and the critical importance of maintaining body weight and LBM in this population, there is an urgent need to determine whether insulin replacement therapy should be instituted for anabolic purposes prior to the actual onset of diabetes and, if so, to ascertain the optimal regimen.

PROTOCOL TITLE: The Impact of Insulin Therapy on Protein Turnover in Pre-Diabetic Cystic Fibrosis Patients

VERSION DATE: 28 June 2021

2.2. Preliminary Data: In a placebo-controlled clinical trial, insulin therapy improved body mass index (BMI) and LBM in patients with very early CFRD (CFRD without fasting hyperglycemia), and this is now standard care for these patients.

2.3. Existing Literature: N/A

3. Study Endpoints/Events/Outcomes

3.1. Primary Endpoint/Event/Outcome: Synthesis rates and relative accumulation of individual proteins (albumin, transferrin, clusterin): the rate of plasma protein synthesis and breakdown can be measured using the amino acid isotopes infused during the isotopic meal study. Fractional synthesis rates of these proteins will be measured from the rate of incorporation of [13C6]Phe. We will purify these proteins by immunoaffinity chromatography and the isotopic enrichment in the respective proteins and plasma Phe will be measured as previously described. The calculation of fractional synthesis rates of these proteins is as described previously using plasma [13C6]Phe as precursor. We will measure the isotopic enrichment in these proteins for 2 weeks after the isotope infusion is discontinued in order to monitor whether the isotope label is retained at a greater or lower rate as a measure of the accumulation of these proteins. If the isotope label is retained longer we will consider it an indication of lower turnover.

3.2. Secondary Endpoint(s)/Event(s)/Outcome(s):

Oxidative damage---In studies in type 1 diabetes, transient insulin deprivation caused accelerated plasma protein oxidative damage. We will assess the extent of oxidative damage by posttranslational modifications and deamidation in new and old isoforms of albumin, transferrin, clusterin, and other proteins. We will determine if insulin treatment prevents or reduces oxidative damage to specific proteins.

Protein Metabolomics—We will use ultra-performance liquid chromatography tandem mass spectrometry to measure 45 amino acids and their metabolites at weeks 0 and 6. It has been shown that amino acids (especially branched chain and aromatic amino acids) are sensitive predictors of developing diabetes in the future, and that branched chain amino acids, aromatic amino acids and several metabolites of amino acids such as citrulline and alpha-amino-adipic acid are highly sensitive to insulin action. These amino acids and metabolites will be a secondary outcome to determine insulin effect.

4. Study Intervention(s)/Investigational Agent(s)

4.1. Description:

PROTOCOL TITLE: The Impact of Insulin Therapy on Protein Turnover in Pre-Diabetic Cystic Fibrosis Patients

VERSION DATE: 28 June 2021

1. Subjects are admitted to the Clinical Research Unit here on the UMN campus in the early morning and 2 IVs are placed.
2. At ~6am subjects are given a priming dose of [15N]-Phe (0.7 mg/kg), followed by continuous infusion over the next 8 hours of 15[N]-Phe (0.7 mg/kg).
3. 2H5-Phe infusion begins at time 0 and continues for 5hr at a variable rate to mimic meal 13C6-Phe Ra.
4. During the second phase of the study, CF patients will have been receiving insulin (basal or bolus) or placebo for 1 month. They will receive their usual insulin/placebo dose during the protein turnover study.
5. To calculate protein dynamics, free amino acids are extracted from plasma using acetic acid and analyzed as their t-butyldimethylsilyl ester derivatives. The molar percent excess (MPE) of phenylalanine isotopes will then be calculated above background

4.2. Drug/Device Handling: Study drug, insulin or placebo (insulin diluent) will be obtained from the manufacturer in standard insulin vials. The investigational pharmacy will cover the label so that the study medication will be blinded.

- IDS #4817

5. Procedures Involved

5.1. Study Design: This double-blind, placebo-controlled trial of insulin therapy in CF youth with abnormal glucose tolerance will assess the impact of 2 different insulin regimens on protein turnover. In Phase 1, stable isotope measurement of meal-stimulated protein flux will be done in CF patients and normal controls, followed by bi-weekly fasting blood draws x2 wks to assess individual proteins. In Phase 2, CF patients will receive once daily basal insulin, 3X daily rapid-acting insulin, or injectable placebo for 6 weeks. After the 1st month, the meal-stimulated protein flux study will be repeated, followed by bi-weekly fasting blood draws x2 wks to assess individual proteins. Power analysis suggests 15 patients are needed per group; 20 are planned to account for drop-outs due to acute illness and non-adherence (although we expect good adherence since the treatment period is short).

5.2. Study Procedures:

Phase 1: Baseline Assessment, No insulin therapy, All CF patients and controls will complete this phase

PROTOCOL TITLE: The Impact of Insulin Therapy on Protein Turnover in Pre-Diabetic Cystic Fibrosis Patients

VERSION DATE: 28 June 2021

Pre-Visit: CF patients will complete a dummy injection experience at the time of consent to see if they are okay with insulin injections. A collection of their latest physical examination will be grabbed from data records to make sure they are healthy. A physical exam, including tanner staging, can be completed at the pre-visit phase for CF patients.

Visit 0 (Baseline):

Meal-stimulated protein flux study (Jello Part): Control participants will be consented and a physical examination will be conducted by the PI at the beginning of this visit, CF patients have this done previously at a pre-visit. The study will start early in the morning (5am). They must have fasted since 8PM the night beforehand and encouraged to drink lots of water to help with IV placement. Two IVs will be placed, one for the isotope infusions and one for blood draws. After a 3 hour intravenous priming infusion, they will consume a jello test meal at time 0 and blood will be periodically sampled for the next 5 hours. The blood draws during the infusions are for cytokines, glucose, c-peptides, insulin, and isotopes. Participants that have CF and their parent/guardian will be asked to complete the Cystic Fibrosis Questionnaire-Revised, a standardized questionnaire created by the cystic fibrosis foundation, during the infusion. Also during the infusion part, a certified dietitian will come in and do a consult in regards to counting carbohydrates. The consult is necessary because it is important to know carb counting when taking insulin. Once the infusion is completed we will give them a meal and take them over to get a DXA scan for determination of lean body mass. Visit 1 (week 1, +/- 1 day): outpatient blood draw to assess individual proteins

Visit 2 (week 2, +/- 1 day): For control patients they will complete an outpatient blood draw to assess individual proteins. End of study participation.

For CF patients: they will complete the same outpatient blood draw and start Phase 2.

Phase 2: Insulin therapy; All CF patients into 3 groups, No controls

Randomized into group (once daily basal insulin, 3x daily rapid acting insulin, or placebo) Insulin (basal or rapid) or placebo, will be supplied by the manufacturer in identical standard insulin vials. Participants will be instructed in subcutaneous injection technique. Study medication adjustments will be made under the supervision of the research teams, who are quite familiar with insulin management in patients with CF, and who will be available at all times for support.

PROTOCOL TITLE: The Impact of Insulin Therapy on Protein Turnover in Pre-Diabetic Cystic Fibrosis Patients

VERSION DATE: 28 June 2021

Visit 3 (Week 6, +/- 7 days): Complete the meal-stimulated protein flux study part again from Phase 1 along with the DXA scan, CFQ-R, and CGM placement. There will not be a dietitian consult at this visit.

Visit 4 (Week 7, +/- 1 day): outpatient blood draw to assess individual proteins and removal of continuous glucose monitor

Visit 5 (Week 8, +/- 1 day): outpatient blood draw to assess individual proteins and end study.

Between Visits:

Study personnel will contact (e.g. telephone, email) patients every three days while insulin is being adjusted and weekly thereafter in addition to their study visits. During these contacts staff will review and adjust (if needed) the medication dose, review hypoglycemia symptoms and management, monitor acute illness or adverse events, provide education, and encourage adherence.

[figure not shown]
Participants will also be asked record their blood glucose levels at random times during the entire study. These need to be recorded to determine clinically if insulin adjustment is necessary.

Patients will receive all usual CF care; study participation will not impact standard-of-care treatment.

PROTOCOL TITLE: The Impact of Insulin Therapy on Protein Turnover in Pre-Diabetic Cystic Fibrosis Patients

VERSION DATE: 28 June 2021

5.3. Study Duration: Each study participant will be in the study for an 8 week duration.

- Anticipated duration to recruit all study participants is 4.5 years.
- The anticipated duration to complete all study procedures, including any long-term follow-up, and data analysis is 5 years.

5.4. Individually Identifiable Health Information: Research participants in this study will sign an Authorization to Use or Disclose Protected Health Information for Research Purposes.

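### Section 5.2 lets the second tracer study move by 7 days either way but does not time the Visit 4 and 5 label-retention draws from it, so elapsed time since infusion is uncontrolled in Phase 2

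*Combined protocol and SAP*

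**What the plan says.** Section 5.2 labels every visit by study week. The second tracer study is "Visit 3 (Week 6, +/- 7 days): Complete the meal-stimulated protein flux study part again from Phase 1". The two draws after it are "Visit 4 (Week 7, +/- 1 day): outpatient blood draw to assess individual proteins and removal of continuous glucose monitor" and "Visit 5 (Week 8, +/- 1 day): outpatient blood draw to assess individual proteins and end study". The Phase 1 counterparts are "Visit 1 (week 1, +/- 1 day): outpatient blood draw to assess individual proteins" and "Visit 2 (week 2, +/- 1 day): For control patients they will complete an outpatient blood draw to assess individual proteins"; for CF patients, "For CF patients: they will complete the same outpatient blood draw and start Phase 2".

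The purpose of the draws is in 3.1: "We will measure the isotopic enrichment in these proteins for 2 weeks after the isotope infusion is discontinued", with longer retention read as lower turnover. The order of events is in 5.1: "After the 1st month, the meal-stimulated protein flux study will be repeated, followed by bi-weekly fasting blood draws x2 wks".

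Section 14 describes a different calendar: four weekly samples after each infusion, with the second infusion at week 8 and sampling over weeks 8-12. It plans summary slopes and a mixed-effects model for longitudinal trends. It does not say whether time is nominal week or actual days since infusion.

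**The concern.** Days since infusion is the time axis of a label-retention measure. In Phase 1 the schedule controls it, because the draws follow Visit 0 with windows of 1 day either way. In Phase 2 the infusion itself can move by a week either way, while the draws keep narrow windows around their own study weeks. The before and after curves of one participant can therefore be sampled at different elapsed times, and a scheduling shift can then pass for a change in retention.

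At stake is the treatment part of Aim 3, namely accumulation of albumin, transferrin and clusterin and any synthesis rate calculated from the same samples. The baseline comparison with healthy controls uses Phase 1 draws only and is not touched. CGM wear is a side issue: under 5.2 the monitor is placed at Visit 3 and removed at Visit 4, so its wear time follows the same gap.

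**Working it through.** **Inputs (5.2).** Take Visit 0 as day 0 and week k as day 7k.

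- Visit 3: 42 +/- 7 = days 35-49
- Visit 4: 49 +/- 1 = days 48-50
- Visit 5: 56 +/- 1 = days 55-57
- Visits 1 and 2: 7 +/- 1 and 14 +/- 1 = 6-8 and 13-15 days after the first infusion

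**The plan's own figure.** At nominal dates, Visit 5 minus Visit 3 = 56 - 42 = 14 days, the 2 weeks in 3.1. Visit 4 minus Visit 3 = 49 - 42 = 7 days. The nominal schedule is sound.

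**Range under the windows as written.**

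- Visit 4 minus Visit 3: 48 - 49 = -1 to 50 - 35 = +15 days
- Visit 5 minus Visit 3: 55 - 49 = 6 to 57 - 35 = 22 days

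Visit 4 falls on or before the infusion day in three of the 15 x 3 = 45 permitted day pairs for Visits 3 and 4: (48, 48), (49, 48) and (49, 49). Only (49, 48) is strictly before.

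**How often Phase 1 can be matched.** A 6-8 day gap to Visit 4 needs Visit 3 between 48 - 8 = 40 and 50 - 6 = 44. A 13-15 day gap to Visit 5 needs Visit 3 between 55 - 15 = 40 and 57 - 13 = 44. So 5 of the 15 permitted Visit 3 days (40-44) can match. The other 10 (35-39 and 45-49) cannot, whichever in-window draw dates are chosen.

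| Visit 3 shift | Gap to Visit 4 (days) | Gap to Visit 5 (days) |
|---|---|---|
| 7 days early | 13-15 | 20-22 |
| 3 days early | 9-11 | 16-18 |
| On time | 6-8 | 13-15 |
| 3 days late | 3-5 | 10-12 |
| 7 days late | -1 to 1 | 6-8 |

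**Effect if time were nominal week (an assumption; Section 14 does not say).** With first-order label loss, the apparent rate is multiplied by actual days / nominal days, whatever the half-life. With Visit 3 three days early or late and draws on their nominal dates, the factors are 10/7 = 1.43 or 4/7 = 0.57 at week 1, and 17/14 = 1.21 or 11/14 = 0.79 at week 2. At opposite window extremes they reach 15/7 = 2.14, 22/14 = 1.57 and 6/14 = 0.43. In Phase 1 they stay within 6/7 to 8/7 (0.86-1.14) and 13/14 to 15/14 (0.93-1.07).

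**Size in retained label.** The documents give no half-life, so a range is assumed. Share left = 0.5^(t/half-life) at the last draw:

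| Assumed half-life (days) | Day 6 | Day 14 | Day 22 |
|---|---|---|---|
| 2 | 13% | <1% | <1% |
| 5 | 44% | 14% | 5% |
| 10 | 66% | 38% | 22% |
| 20 | 81% | 62% | 47% |

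**Effect if time were actual days.** The misdating goes, but the spacing of the points still matters. For a three-point log-slope with equal, independent errors, SE is proportional to 1/sqrt(Sxx).

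- Days {0, 7, 14}: Sxx = 98.
- Visit 3 three days late, {0, 4, 11}: mean 5, Sxx = 25 + 1 + 36 = 62; SE ratio sqrt(98/62) = 1.26.
- Corner case {0, 0, 7}: Sxx = 49 - 49/3 = 32.7; SE ratio sqrt(98/32.7) = 1.73.

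Early Visit 3s spread the points and lower this SE, provided that the label is still measurable.

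**The case against.** The best defence is that 5.2 names no anchor at all. Sections 3.1 and 5.1 place the draws after the infusion and over 2 weeks, so sensible staff would count from Visit 3. This stands in part. A reader might infer that the protocol calls for a draw before the infusion. It does not: the order stated in 5.1 excludes that, and the -1 and +22 day values are corners of the windows. But for 10 of the 15 permitted Visit 3 days, counting from Visit 3 puts Visits 4 and 5 outside their own written windows, so intent and schedule cannot both be met. The figure after the visit list was not available for this check. If it states an anchor, the text should say the same.

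A reader might also infer that the treatment comparison is biased. The documents do not support that. Allocation is randomised, participants and clinic staff are blinded (8.3), and the window is symmetric, so timing scatter should fall alike on all arms and act mainly as noise. Bias would need Visit 3 timing to differ by arm, and nothing shows that.

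The large rate factors need opposite window extremes together with analysis by nominal week, which Section 14 does not specify. The CGM point is modest. Poisson regression can allow for unequal wear time, although Section 14 states no exposure term, and Section 14 also plans CGM over weeks 1-12, so 5.2 alone does not settle wear time.

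**Conclusion.** The point holds as a scheduling gap that should be fixed. On the literal reading of the week labels, Phase 2 draws can fall -1 to +15 and 6 to 22 days after infusion, against 6-8 and 13-15 in Phase 1, and two thirds of the permitted Visit 3 days (10 of 15) cannot reproduce the Phase 1 timing. The direct harm is to each participant's before/after retention measure; between arms it is added noise.

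A reader might take this as a threat to the trial's main result. It is not one under Section 14, where the powered primary endpoints (change in QP and QPT) come from the tracer study day and do not depend on the later draws. Section 3.1 does call the individual-protein measures primary, whereas Aim 3 and Section 14 treat them as exploratory. If 3.1 governs, the point weighs more.

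The day ranges rest only on Visit 0 as day 0 and week k as day 7k. The rate factors also assume first-order loss and nominal-week analysis, the retained-label table an assumed half-life, and the SE ratios a three-point log-linear fit.

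**What to change.** 1. In 5.2, define Visit 4 as 7 +/- 1 days and Visit 5 as 14 +/- 1 days after the actual Visit 3 infusion date. The draws then fall 6-8 and 13-15 days after infusion, as in Phase 1.
2. In Section 14, prespecify actual days since the end of infusion, not nominal week, as the time variable in the retention models, and apply this to participants already studied. Section 16.2 says that efficacy data are not reviewed until study end, so the rule can still be set beforehand. It cannot recover retention information from a draw taken on or before the infusion day.
3. State that CGM rates use actual wear time as exposure.

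The cost is small: no added visits or samples, only recorded dates. The downside is that Visit 5 could fall anywhere from day 35 + 13 = 48 to day 49 + 15 = 64, up to 8 days past the 56 days of an 8-week participation. The participation statement in 5.3, the 6-week treatment statement in 5.1 and the Section 14 calendar (four weekly samples, weeks 8-12) must therefore be reconciled with the new definition.

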Analysis of secondary protein turnover endpoints will be exploratory extensions of previous work (37, 38, 57, 58). For the 3 proteins of interest (albumin, transferrin, clusterin), both the fractional synthesis rate and relative isotopic enrichment (ratio of isotopic enrichment to the baseline enrichment) will be calculated from each of the 4 weekly blood samples after both the week 0 and week 8 labeled-infusion studies. At these same points we will also assess the accumulation of damaged proteins, since

PROTOCOL TITLE: The Impact of Insulin Therapy on Protein Turnover in Pre-Diabetic Cystic Fibrosis Patients

VERSION DATE: 28 June 2021

oxidative stress is likely to be reduced during insulin therapy. The baseline (wks 0-4) comparison will be between CF participants and healthy controls, while the comparison of the treatments will use measurements from both weeks 0-4 and 8-12. The profiles of these rate changes over time will be compared visually, by summary measures such as slope if applicable, and by mixed effects linear model for longitudinal trends, with participants treated as a random effect to model the correlation between repeated observations from the same subject.

Protein metabolomics will be assessed during the in-patient studies at week 0 and week 8. The baseline comparison will be between CF participants and healthy controls, while the comparison of the treatments will use changes from week 0 to week 8. The comparison of protein metabolomics will use principal components analysis of the baseline protein and metabolite measurements to find separated clusters of CF participants versus healthy controls, and principal components analysis of the week 8 measurements to compare clusters between the three treatment groups.

Secondary mechanistic endpoints are measured weekly during both baseline and intervention phases: 3-point glucose profiles, mean and MAGE plasma glucose will be measured at weeks 1-12 using CGM. We will use a mixed-effects linear model to compare these longitudinal profiles of plasma glucose between treatments, adjusting for the appropriate baseline value and treating participants as a random effect to model the correlation between repeated observations from the same participant.

The safety analysis will estimate and compare rates of hypoglycemia and subclinical hypoglycemia (identified from CGM) between treatments using Poisson regression. In addition, rates of non-adherence will be compared between treatments.

Power Analysis

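### Section 14 plans weekly, baseline-adjusted CGM glucose, but the Section 5.2 schedule names one sensor wear, about four weeks into treatment

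*Combined protocol and SAP*

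**What the plan says.** **Schedule (protocol Section 5.2).** CGM appears twice. At Visit 3 (week 6, ±7 days) the instruction is "Complete the meal-stimulated protein flux study part again from Phase 1 along with the DXA scan, CFQ-R, and CGM placement". At Visit 4 (week 7, ±1 day) it is "outpatient blood draw to assess individual proteins and removal of continuous glucose monitor". Visit 0 lists the flux study, CFQ-R, dietitian consult and DXA; Visits 1 and 2 list blood draws. None of the three names a sensor. Treatment begins at Visit 2 (week 2), when CF participants "they will complete the same outpatient blood draw and start Phase 2". Section 5.1 gives 6 weeks of treatment and Section 5.3 gives 8 weeks of participation.

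**Analysis (Section 14).** The mechanistic glucose endpoints are described as weekly in both the baseline and the intervention phase, with CGM mean glucose and MAGE at weeks 1-12. Arms are to be compared by a mixed-effects model of the longitudinal profiles, "adjusting for the appropriate baseline value and treating participants as a random effect to model the correlation between repeated observations from the same participant". For safety, "The safety analysis will estimate and compare rates of hypoglycemia and subclinical hypoglycemia (identified from CGM) between treatments using Poisson regression".

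**Other glucose and hypoglycemia data.** Glucose is among the blood measurements in the flux study at Visit 0, and that study is repeated at Visit 3. Between visits, "Participants will also be asked record their blood glucose levels at random times during the entire study". Staff contact participants every third day during dose adjustment and weekly afterwards, and review hypoglycemia symptoms each time (Section 5.2). Adverse events go on case report forms (Section 16.2).

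**The concern.** The mixed model needs a pre-treatment CGM value and several CGM weeks per participant. The visit schedule supplies neither. An analyst following Section 14 would have to invent a different analysis after the data are in, and Section 14 does not say which.

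The safety side matters more. Section 16.2 names severe hypoglycemia as the one significant risk tied directly to the study, and Hypothesis 2 includes a safety claim for once-daily basal insulin. If CGM-identified events are counted only from about week 4 of treatment onward, the comparison says nothing about such events earlier, when dose adjustment is very likely most frequent. Nothing in Section 14 limits the resulting rate to that late week.

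Section 14 also plans to relate change in protein turnover to CGM mean glucose and MAGE. With the sensor placed at Visit 3, that glucose would be recorded from the second flux study onward, not over the treatment that preceded it.

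**Working it through.** **1. The plan's own figure.** Section 14 gives CGM at weeks 1-12. Section 5.3 gives 8 weeks of participation, so weeks 9-12 have no place in the schedule. The 12-week span cannot be reproduced from Section 5.2.

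**2. Coverage from the visit schedule.** Nominal wear is week 6 to week 7, that is 1 week.

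| Period | Weeks | CGM weeks named | Share |
|---|---|---|---|
| Section 14 plan | 12 | 1 | 1/12 = 8% |
| Participation | 8 | 1 | 1/8 = 12.5% |
| Treatment (weeks 2-8) | 6 | 1 | 1/6 = 17% |
| Baseline (weeks 0-2) | 2 | 0 | 0% |
| Treatment before Visit 3 (weeks 2-6) | 4 | 0 | 0% |

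Cutting the Section 14 range to weeks 1-8 leaves the numerator at 1, so relabelling does not restore a baseline or repeated weeks.

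**3. Time on treatment at placement.** With the windows, Visit 2 is day 13-15 and Visit 3 is day 35-49. Nominal: 42 − 14 = 28 days. Range: 35 − 15 = 20 to 49 − 13 = 36 days.

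**4. Wear time.** Nominal wear is 49 − 42 = 7 days. If Visit 4 is held to calendar week 7 (day 48-50), wear runs from none (48 − 49 < 0) to 50 − 35 = 15 days. If Visit 4 is counted from Visit 3, wear is 6 to 8 days. The text does not say which applies. In either case exposure varies between participants.

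**5. Precision of a CGM event-rate comparison.** The documents give no event rate, so 0.25 to 2 events per person-week is assumed, with pure Poisson variation and equal rates in two arms of n.

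SE(log rate ratio) = √(2 / (rate × n × weeks)); 95% factor = exp(1.96 × SE).

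Example with n = 15 and rate 1. One week gives 15 events per arm, SE = √(2/15) = 0.365, factor 2.05. Six weeks give 90 events, SE = √(2/90) = 0.149, factor 1.34.

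| Assumed rate per person-week | n = 15, 1 week | n = 15, 6 weeks | n = 20, 1 week | n = 20, 6 weeks |
|---|---|---|---|---|
| 0.25 | 4.18 | 1.79 | 3.45 | 1.66 |
| 0.5 | 2.75 | 1.51 | 2.40 | 1.43 |
| 1 | 2.05 | 1.34 | 1.86 | 1.29 |
| 2 | 1.66 | 1.23 | 1.55 | 1.20 |

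Whatever the rate, the standard error is √6 = 2.45 times larger with one week than with six. Overdispersion would widen every interval.

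**The case against.** **A baseline sensor may have been intended.** The Visit 3 sentence says the Phase 1 study is done again "along with the DXA scan, CFQ-R, and CGM placement". DXA and CFQ-R were both done at Visit 0, so the list can be read as repeating Phase 1, and Section 14 speaks of both phases. A figure in Section 5.2 is also not available here. This stands as a possibility, so a reader should not take it as settled that the sensor is worn only once. But Visit 0 spells out DXA and CFQ-R without CGM, and Visit 1 has no removal step to match Visit 4. Even with a baseline wear there would be one week before treatment and one on it, which allows a single adjusted comparison and not weekly profiles.

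**There are data.** This also stands. One on-treatment week per participant supports a randomized comparison between arms, and timed plasma glucose exists from both flux studies. It would be wrong to infer that the CGM analysis has nothing to work on, or that self-readings are the only other glucose source. What is missing is the CGM baseline and the repeated weeks.

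**Hypoglycemia is captured elsewhere.** In Section 14 the reference to CGM may qualify only the subclinical events. Symptomatic events can be picked up throughout treatment from contacts, self-recorded glucose and adverse event forms. The certain gap is therefore CGM-identified events before Visit 3. A comparison of rates between randomized arms does not need a baseline rate either, so the lost treatment time is the real loss.

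**Dose adjustment may not all be missed.** A reader might infer that the sensor misses every dose change. The documents do not support that: no end date for adjustment is given, and doses can still be changed at the weekly contacts.

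**Conclusion.** Sections 5.2 and 14 contradict each other, and the CGM model in Section 14 cannot be fitted on the schedule in Section 5.2. The schedule gives about 1 of 6 treatment weeks (17%), no baseline week and no repeated weeks. CGM-identified hypoglycemia is unobserved for a nominal 28 days of treatment (20 to 36 with the windows), which very likely include the period of frequent dose adjustment.

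This rests on reading the visit list as complete; an unlisted baseline sensor would add one week and leave the early-treatment gap. The loss of precision depends on an assumed event rate: with 15 per arm and no overdispersion, the 95% rate-ratio factor is 4.18 to 1.66 for one week, against 1.79 to 1.23 for six, over 0.25 to 2 events per person-week.

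The primary protein-turnover comparison is untouched. The change should be made, but it is not critical to the trial.

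**What to change.** Reconcile Sections 5.2 and 14 before unblinding, according to what is actually done.

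- **If there is one wear:** replace the longitudinal CGM model with one on-treatment summary per participant (mean glucose, MAGE), compared between arms without a CGM baseline term. Analyse CGM-identified hypoglycemia by Poisson regression with actual wear time as the offset. State that the result applies to that week only and does not support a whole-treatment safety claim under Hypothesis 2.
- **If a baseline sensor was placed:** write placement and removal into Visits 0 and 1, and use a single baseline-adjusted comparison. The limits on the safety claim stay.
- **In both cases:** name the source for symptomatic hypoglycemia over the whole treatment period, namely the contact records, self-recorded glucose and adverse event forms already collected. Correct the Section 14 week numbers, and say whether Visit 4 is timed from Visit 3 or from the calendar.

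The cost is a wording change and use of data already being collected; the price is a narrower CGM safety conclusion. Adding a baseline sensor that has not been used so far, or weekly 3-point profiles at fixed times, would be new collection. Section 9.1 reports 40 CF patients already consented, so it could come too late for many of them.
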